15.0 DISCONTINUATION OF TREATMENT AND WITHDRAWAL OF PATIENTS

The reasons a patient may discontinue or be withdrawn from the study include, but are not limited to, adverse event, disease progression, patient request, protocol violation, patient noncompliance, study termination by the Sponsor, and subject transition to commercial pexidartinib (Turalio™). When a patient discontinues or is withdrawn, the investigator will notify the Sponsor and should perform the procedures indicated in the End of Study visit column in the study flow chart 7–30 days after the last dose of study drug and prior to initiation of any new anti-cancer therapy. Follow-up information will be obtained for patients who discontinue their participation in or are withdrawn from the study. Patients withdrawn from the study will be replaced at the discretion of the medical monitor and the investigator. Test article administration may be discontinued for an adverse event or at the discretion of the investigator.

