For the five disease-specific Extension cohorts, a sample size of 10 patients is considered the minimum sample size required to test the hypothesis that single agent pexidartinib can provide a clinical benefit in this patient population. For each Extension cohort, we plan to test the hypothesis of no clinical benefit against the hypothesis that at least 30% of patients achieve a clinical benefit. With a sample size of 10 patients per group, we will have 85% power at a 0.10 significance level to declare pexidartinib worthy of further study if at least 2 patients achieve clinical benefit. For this study, clinical benefit is defined as either CR/PR or PFS ≥ 6 months. If fewer than 2 patients achieve clinical benefit within a disease group, pexidartinib will not be considered worth of further study within that disease. Depending on the response in the 10-patient cohort, the sample size for a specific cohort may be increased by 30 additional patients (to approximately 40 patients total) if those data are determined to be necessary to design additional studies in that indication.

For the miscellaneous Extension cohort, a sample size of 20 patients will be used, as the tumor types are anticipated to be rare. The sample size is not determined by any statistical power considerations. Accordingly, the potential clinical benefit will be evaluated on a per-patient basis. If one or more partial responses are observed in patients in the miscellaneous cohort, additional patients (up to 20 total additional patients) may be recruited if needed to profile the tumor responses in the specific (or related) indications.

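### Discretionary replacement of withdrawn patients in the open-label extension cohorts adds chances to reach a fixed go threshold of 2 that was designed for 10 patients

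*Combined protocol and SAP*

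**What the plan says.** Section 15.0 gives a non-exhaustive list of reasons for leaving the study, among them "adverse event, disease progression, patient request, protocol violation, patient noncompliance". Later in the same paragraph it says: "Patients withdrawn from the study will be replaced at the discretion of the medical monitor and the investigator". The sentence is not restricted by reason, number, timing or study phase, and no other section restricts it.

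Section 24.6 sets a formal rule for each of the five disease-specific extension cohorts. The null is no clinical benefit, without a number; the alternative is a benefit rate of at least 30%. The claim is "With a sample size of 10 patients per group, we will have 85% power at a 0.10 significance level", and the action is "to declare pexidartinib worthy of further study if at least 2 patients achieve clinical benefit". Clinical benefit means CR/PR, or PFS of 6 months or more. The no-go side is also explicit: "If fewer than 2 patients achieve clinical benefit within a disease group", the drug is not taken further in that disease. The section does not say whether a replaced patient, or the replacement, counts toward the rule.

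Two other places bear on this. Section 24.2 defines who is evaluable for efficacy: patients with measurable disease who have had a scan after baseline or who stopped early for progression. Section 9.2 gives the cohort size as approximately 10.

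**The concern.** In these cohorts some withdrawals are themselves outcomes. A patient who leaves for progression before 6 months without CR or PR has failed the endpoint. The trial is open-label, so the people who decide on replacement know this.

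The go rule is a bare count with no denominator attached. Each replacement gives another chance to reach 2, and the threshold does not move. At stake is the go/no-go reading for each disease: the more failures are replaced, the likelier a go becomes whatever the drug does.

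A second route concerns patients who leave for toxicity or another non-progression reason before a first scan after baseline. They fall outside the evaluable set in Section 24.2, so a cohort refilled to 10 evaluable patients could omit them altogether.

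The point is confined to the disease-specific extension cohorts. In dose escalation, Section 16.4 already counts first-cycle DLTs in all patients, and the miscellaneous cohort has no count rule of this kind.

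**Working it through.** **Inputs.** From Section 24.6: n = 10, threshold 2, alternative 30%, power 85%, level 0.10. Not in the documents, and so assumed: the true benefit rate p under the null (3%, 5% and 10% shown) and the number of replacements k (0 to 4 shown).

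**Formula.** With n treated patients, P(go) = P(X ≥ 2) = 1 − (1−p)^n − n·p·(1−p)^(n−1).

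**Step 1: the plan's own figure.** For n = 10 and p = 0.30, P(go) = 1 − 0.0282 − 0.1211 = 0.8507. This reproduces the 85%. Thresholds of 1 and 3 would give 0.972 and 0.617, so the design is at least 2 of 10.

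**Step 2: the 0.10 level.** For n = 10 and p = 0.05, P(go) = 1 − 0.5987 − 0.3151 = 0.0861. Solving P(go) = 0.10 gives p = 5.45%. The stated level therefore holds at n = 10 only if the null rate is at most about 5.45%.

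**Step 3: replacements against an unchanged threshold.** With k replacements all counted, n = 10 + k. Adding patients only while the count is below 2 gives the same probability, because the count can only rise. A cohort still below 2 has at least 9 patients without benefit, so four replacements are within reach if that many have withdrawn.

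| True rate | n = 10 | n = 11 | n = 12 | n = 14 |
|---|---|---|---|---|
| 3% | 0.0345 | 0.0413 | 0.0486 | 0.0645 |
| 5% | 0.0861 | 0.1019 | 0.1184 | 0.1530 |
| 5.45% | 0.1000 | 0.1180 | 0.1366 | 0.1756 |
| 10% | 0.2639 | 0.3026 | 0.3410 | 0.4154 |

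The largest true rate that keeps P(go) at or below 0.10 falls from 5.45% at n = 10 to 4.95% at n = 11 and 3.87% at n = 14.

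**Step 4: patients lost before a first scan.** Suppose a fraction q of treated patients, all without benefit, leave the evaluable set and the cohort is refilled to 10 evaluable. The benefit rate among those counted is then p/(1−q). At p = 5%:
- q = 10%: rate 5.56%, P(go) = 0.103
- q = 20%: rate 6.25%, P(go) = 0.126
- q = 30%: rate 7.14%, P(go) = 0.157

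Dropping a failure does not by itself alter a count of successes. The rise comes from refilling the cohort, so this is the same mechanism as in Step 3.

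**The case against.** **No null rate is stated.** Taken literally, no benefit means p = 0, and P(go) is then 0 at any n. At 3%, four replacements leave it at 0.0645. At 10% the rule is at 0.264 with no replacement. A single replacement moves P(go) across 0.10 only if the true rate lies between 4.95% and 5.45%. This stands. A reader might infer that the rule simply loses its stated error rate; the documents do not support that, because they do not fix the rate at which the 0.10 is to be judged.

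**Progressors stay evaluable.** A reader might infer that a progressor can be replaced and removed from the analysis. Section 24.2 keeps such patients in the evaluable set, so they cannot be removed. It does not stop further patients being enrolled against the same threshold, and it does not cover withdrawals for other reasons before a first scan.

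**A narrower intent is plausible.** Section 15.0 uses both discontinue and withdraw, and the replacement sentence mentions only withdrawn patients. Treatment until progression is the planned course, so replacing every progressor would give enrolment no natural end. That is fair, but the text does not state a narrower rule.

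**The stakes are modest.** Section 24.5 makes the analyses mostly descriptive, and Section 24.6 opens by saying that patient numbers do not rest on power. It also calls 10 the minimum. Section 7.0 links further development to benefit-risk, not to this count alone. Power rises as well, from 0.851 to 0.936 with three more patients. All true; yet Section 24.6 does state a test, a level and a no-go for these cohorts.

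**Conclusion.** The concern holds as a design weakness of moderate weight. Replacement is discretionary, can be decided with the outcome known, and has no limit by reason or number, while the go threshold stays at 2. At an assumed 5% true rate, P(go) rises from 0.086 to 0.153 with four replacements. At the 5.45% that matches the stated level it rises from 0.100 to 0.176. At 3% it stays below 0.10 up to 14 patients. At 10% it runs from 0.264 to 0.415, and most of that excess comes from the unstated null rate, not from replacement.

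These sizes rest on the assumed rates and numbers of replacements. The documents do not show that any patient was replaced, so the inflation is potential.

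A reader might also infer that false positives are most likely in the fastest-progressing diseases because more patients leave. The documents do not support this. Benefit includes PFS of 6 months or more, so fast progression would suggest a low background rate, and by the table four replacements at 3% add 0.030 while one at 10% adds 0.039.

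**What to change.** - **Section 15.0:** state that, in the disease-specific extension cohorts, patients who received study drug are not replaced for the purpose of the go rule.
- **Section 24.6:** apply the rule of at least 2 to the first 10 treated patients in order of first dose. Count anyone without documented benefit as no benefit, and report any additional patients descriptively. State the null rate behind the 0.10 level.
- **Section 24.2:** note that the go-rule denominator is all treated patients under that rule, and is distinct from the efficacy-evaluable set.

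With n held at 10, power stays at 0.851 and P(go) is 0.086 at 5% and 0.100 at 5.45%. The optional expansion by 30 patients in Section 24.6 is unaffected.

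The cost is a few sentences in three sections. The downside is that an early dropout without a scan counts as no benefit, which makes a go slightly harder. If more than 10 patients had to count, the threshold would have to rise to 3. At n = 12 that gives P(go) = 0.020 at 5% but cuts power to 0.747, so fixing the first 10 is the better choice.

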16.0 TEST ARTICLE

16.1 Test Article Administration

Test article (study drug) will be administered only to patients who have signed and dated an informed consent form. Test article will be administered on days 1 through 28 or longer in the fasting state with 240 mL (8 oz.) of room-temperature water. The patient should fast at least 2 hours before administration and 1 hour after administration of the test article. Patients will be permitted to eat a low-fat snack (e.g., crackers, toast, tea) during the fasting period if needed. Test article will be taken orally by swallowing the capsules. For patients with tumors of the head and neck area who may have difficulty swallowing capsules, test article may be administered by emptying the contents of the dose (e.g., 3 x 200 mg capsules in the morning, and 2 x 200 mg capsules in the evening for a total daily dose of 1000 mg/day) into an empty glass.

Approximately 6 ounces of orange juice, apple juice, or cola should be added to the glass, stirred vigorously with a spoon and the patient should drink the contents, add 2 additional ounces to the glass, stir again and drink the remaining contents. The entire dose should be consumed within 30 minutes and the capsule shells should be discarded in a bio-disposable hazard bag provided by the site. NOTE: The Plexxikon Medical Monitor must be consulted prior to implementation of this alternative method of test article administration.

Test article administration will start on C1D1 and should be taken once daily for the initial cohort. Subsequent cohorts may utilize a twice daily dosing regimen, with study drug being administered at approximately 12-hour intervals. On PK collection C1D1 and C1D15, the patients will be administered pexidartinib capsules at the clinical site. The time of the administration will be recorded. On non-PK collection days, patients will administer the study drug at home. Missed doses (i.e., outside of a + 2-hour window) should be skipped and not administered as a double dose at the next administration. Patients who vomit their dose should be instructed to NOT to make up that dose. Patients should take precautions to prevent accidental ingestion of or exposure to investigational drug by family members or other cohabitants.

Food-Effect Assessment:

Once the optimal dose has been identified at steady state (C1D15) in the fasted state, a subset of patients may be studied in this trial to assess the effect of food on pexidartinib exposure. For active patients who consent to this optional procedure, the food-effect assessment will only be initiated on or after the C1D15 visit. C1D15 will remain a fasted PK analysis visit, i.e., PK samples should be obtained in the fasted state at predose (AM) and 1, 2, 4 and 6 hours postdose. After electing to participate in this optional procedure, at their next clinic visit these patients will have PK samples drawn prior to the morning dose and then 2 and 4 hours post-dose in the fasting state (with a low-fat snack if needed, as above). This will serve as a baseline steady state PK assessment of pexidartinib administered in the fasting state. The patients should then be instructed to begin dosing study drug with meals, beginning with the evening dose on the day of this visit (if a BID dosing regimen is being used). Each pexidartinib dose should be taken with food (for example breakfast and dinner). The dose should be administered within 30 minutes of beginning the meal, but not before the meal. The patients will be asked to return to the clinic 2–4 weeks after the food-effect assessment has begun. At this visit, a total of 3 blood samples (predose that morning, 2 and 4 hours post-dosing with a meal) will be drawn for analysis of pexidartinib exposure.

After the effect of food on pexidartinib exposure has been determined, all patients in this trial will be informed whether or not to take study drug with meals.

16.2 Packaging and Labeling

Pexidartinib-HCl capsules (100 mg or 200 mg strength of the active free base of pexidartinib) are manufactured, packaged, and labeled according to GMP and GCP.

16.3 Storage and Stability

Pexidartinib-HCl capsules will be stored at the clinical site, as indicated on the study drug label, i.e., room temperature (not above 25°C).

Patients will be requested to store the pexidartinib at the recommended storage conditions noted on the label out of the reach of children or other cohabitants.

16.4 Dose Escalation

At least three and up to six patients will be enrolled in each dose level using 100% dose increments for each level in the absence of Grade 2 or greater drug-attributable toxicity. In each cohort (and following the one-week run-in period for applicable patients), the first patient will be observed for at least one week before additional patients in that cohort are treated with pexidartinib. Following the one-week run-in period for applicable patients, upon the occurrence of Grade 2 or greater toxicity, in the absence of DLT, dose escalation will proceed sequentially by up to 50% increments. Following the one-week run-in period for applicable patients, if one DLT is observed in one of the first 3 patients during the first cycle in a given cohort, at least 6 patients will be treated at that dose. Following the one-week run-in period for applicable patients, if DLT is observed in 2 or more of 6 patients at a dose level, then the next lower dose level will be expanded or an intermediate dose level will be introduced. Dose escalation will only be permitted if adequate safety and tolerability have been demonstrated at the previous lower dose for 28 days for the first 3 patients. The DLTs observed in all patients in the first cycle will be taken into account when evaluating the safety of a given dose level to support dose escalation or selection of a recommended Phase 2 dose. Dose escalation decisions will be made during teleconferences attended by the medical monitor and appropriate personnel from all participating sites.

Dose Limiting Toxicities during the first 28 days of treatment are defined as follows:

- Any CTCAE (version 4) Grade 4 toxicity (Grade 4 neutropenia for ≥ 3 days)
- Any CTCAE Grade 3 toxicity other than Grade 3 lymphopenia
- CTCAE Grade 2 vomiting within 2 hours of study drug administration on 3 consecutive days despite optimal anti-emetic therapy
- If, for any reason, either the Principal Investigator or Sponsor deems further dose escalation inappropriate

The specific criterion for Grade 2 vomiting is based on the observations in the dog toxicity studies; vomiting may preclude adequate oral absorption of study drug. The justification for the exemption of Grade 3 lymphopenia is based on the following: a) modest lymphopenia of uncertain mechanism was observed in the 28-day GLP rat repeat dose toxicology study, but only at significant dose and exposure multiples vs. the clinic, b) asymptomatic and clinically nonsignificant lymphopenia is a common finding in patients with advanced solid tumors, c) patients may exhibit continuing or even worsening asymptomatic lymphopenia during clinical trials with no clinical consequence, and d) the clinical risk of G3 lymphopenia, in the absence of concurrent atypical infections, is minimal.

The MTD is defined as the dose at which ≤ 1 of 6 patients experience a DLT during Cycle 1, with the next higher dose having at least 2 of the up to 6 patients experiencing a DLT during Cycle 1.

No dose reductions are to be made during Cycle 1, which is the primary evaluation period for safety. Dosing will be discontinued based on DLT criteria noted above. If a patient has a documented objective clinical benefit despite having an individual DLT, continued dosing at a reduced dose may be allowed, after consultation with the FDA.

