
	
At the recommended Phase 2 dose (RP2D), a total of six Extension cohorts of approximately 10 patients each (except for the miscellaneous cohort, which will include up to approximately 20 patients) will be enrolled and followed for safety and tumor response as assessed by radiographic imaging. These six cohorts consist of 1) mucoepidermal carcinoma (MEC) of the salivary gland, 2) pigmented villo-nodular synovitis (PVNS), 3) GIST, 4) anaplastic thyroid carcinoma (ATC), 5) solid tumors with documented malignant pleural or peritoneal effusions, and 6) miscellaneous tumor types for which a scientific rationale exists for treatment with pexidartinib. For PVNS patients, imaging will also be performed approximately 30 days and 12 weeks after last study drug.
 
Patients will be monitored throughout the study for adverse reactions to the drug formulation and/or study procedures.
 
For the dose escalation cohorts, clinical laboratory assessments (hematology, chemistry, and urinalysis) will be performed at screening, C1D8, C1D15, and at the beginning of each subsequent 28 day cycle for those patients who continue on therapy, and at study completion or upon early withdrawal. Urinary, blood and serum biomarkers of response will be evaluated on C1D1, C1D8, and C2D1.
 
Blood pressure, respiratory rate, pulse, and temperature will be measured at screening and predose at each study visit except for C1D2 and C1D16. Blood pressure and pulse will also be monitored at 1 and 4 hours postdose on C1D1.
 
Triplicate ECGs (within 2 minutes apart) will be obtained at screening, prior to dosing on C1D1, and at 2, 4, and 6 hours postdose on C1D1 and C1D15.
 
A physical examination will be performed for each patient at screening, C1D8, C1D15, C2D1, and then monthly while continuing study drug administration, and at study completion or upon early withdrawal.
 
For the Extension cohorts, a simplified study plan will be used, as detailed in the study flow chart. Patients enrolled after the implementation of Amendment 8 will complete two patient reported outcome (PRO) instruments: the Western Ontario and McMaster Universities Osteoarthritis Index (WOMAC[®]) and the Numeric Rating Scale (NRS) for PVNS Symptoms questionnaire. These will be completed predose at the clinic on C1D1, C1D15, C2D1, and monthly thereafter while continuing study drug administration, and at the End of Study visit. In addition, these patients will complete the NRS for PVNS Symptoms questionnaire on an outpatient basis for 6 consecutive days (Day -6 to Day -1) prior to each monthly clinic visit on C1D1, C2D1, C3D1, etc. while continuing study drug administration.
 
The visit schedule for extension patients will be changed to every 12 weeks/3 cycles (with an option to complete on-site visits every 24 weeks/6 cycles if local safety laboratory testing and telephone check-ins are completed 12 weeks after each on-site visit) after a subject has completed at least C40 and if there are no ongoing safety or treatment issues. Imaging will be performed every 24 weeks/6 cycles, and PK, Urinalysis, and ECOG will be discontinued.

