13.9 Dose Modification (Dose Escalation Cohorts)

Reduction/interruption of dosing for adverse events may take place any time. Below are general guidelines for dosage modification for pexidartinib-related toxicities as well as guidelines for their management.

For toxicities which are considered by the investigator unlikely to develop into serious or life-threatening events (e.g., alopecia, altered taste, etc.), treatment should be continued at the same dose without reduction or interruption. In addition, if any Grade 1 toxicity occurs, treatment should be continued at the original dose without interruption. If drug-related Grade 2 toxicity occurs, the Sponsor should be notified, and the investigator may discontinue or interrupt treatment with pexidartinib if it is considered to be medically appropriate. If dosing is interrupted, treatment at the same dose may be resumed once toxicity is \leq Grade 1.

If Grade 3 or 4 drug-related toxicity occurs, immediate treatment interruption will be followed by a selective dose reduction depending on the types of toxicity, and based on discussion and agreement between the investigator and Sponsor after recovery of the toxicity to at least Grade 1. pexidartinib re-challenge after interruption of dosing may occur only if the investigator and Sponsor agree that it is in the best interest of the patient. In addition, the patient's ECOG performance status must be 0–2. Following re-challenge at a modified dose, study visits will occur at approximately one month intervals for assessment of safety and PK, and two month

intervals for assessment of tumor response or progression. Dosing interruptions longer than 3 weeks should generally result in discontinuation from the study, unless the patient has demonstrated a clinical benefit from therapy and would like to continue dosing with study drug. All adjustments should be made in consultation with the Medical Monitor.

If treatment with pexidartinib is interrupted due to bone marrow toxicity in Cycle 2 and beyond, growth factors may be used. However, growth factors should not be used concomitant with study drug dosing, as it will interfere with the assessment of drug toxicity.

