24.0 STATISTICAL ANALYSIS

24.1 Safety Analysis

All patients in all cohorts who received study medication will be considered evaluable for safety regardless of their duration of treatment.

The objective of the dose escalation is to determine a dose of pexidartinib for which the rate of DLTs is less than 33%. Safety variables to be analyzed are AEs, laboratory test results (hematology, clinical chemistry, coagulation parameters, and urinalysis), ECG, and vital signs. Adverse event terms recorded on the CRFs will be mapped to preferred terms using the Medical Dictionary for Drug Regulatory Activities (MedDRA®) version 7.1 or higher. All AEs will be summarized for each dose group according to the system organ class and preferred term within the organ class. Adverse events will be tallied for overall frequency (number and percentage of subjects), worst reported severity, and relationship to study drug for each preferred term per subject. Serious adverse events will be similarly summarized. Listings of deaths, SAEs, and AEs leading to early termination of study treatment or premature withdrawal from study will also be provided. In addition, all events meeting the criteria of a DLT will be tabulated as a separate listing by subject and dose group. Laboratory variables will be examined using mean change in value from baseline to scheduled time points for each pexidartinib dose group. Laboratory values

will also be categorized according to their CTCAE (version 4) toxicity grade and tabulated by worst on-study toxicity grade and pexidartinib dose group. The baseline value of a variable is defined as the last value obtained on or before the date and time of the first pexidartinib dose. Concomitant medications will also be summarized.

ECG/QT Analysis:

All ECG information will be listed by patient, including change from baseline for numeric ECG parameters (based on means of the triplicate assessments). Summaries by time-point will be provided for absolute and change from baseline numeric ECG parameters (including categorical summaries for QTc absolute and change from baseline). Plots of mean ECG data and their change from baseline over time will be provided. For each of the time points, the available triplicate QTc values will be averaged for all analyses.

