26.2 Recording and Reporting

A patient's AE or SAE can occur from the time the patient receives the first dose of study drug until the patient's End of Study visit.

The investigator must follow-up on all drug-related AEs, SAEs, and other reportable information until the events have subsided, returned to baseline, the patient has initiated any other anticancer treatment, or in case of permanent impairment, until the condition stabilizes.

All AE and SAEs must be recorded on source documents. All AEs and SAEs for patients who are not screen failures will be recorded in the CRFs.

AEs should be based on the signs or symptoms detected during the physical examination and on clinical evaluation of the patient. In addition to the information obtained from those sources, the patient should be asked the following nonspecific question: "How have you been feeling since your last visit?" Signs and symptoms should be recorded using standard medical terminology.

Any unanticipated risks to the patients must be reported promptly to the IRB/IEC.

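### The DLT rule counts Grade 3 neutropenia of any duration but Grade 4 neutropenia only from 3 days, and no text says how a shorter Grade 4 event is classified

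*Combined protocol and SAP*

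**What the plan says.** Section 16.4 defines DLTs over the first 28 days in four bullets, and the Synopsis (Stopping Rules) lists the same four.

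- Bullet 1: "Any CTCAE (version 4) Grade 4 toxicity (Grade 4 neutropenia for ≥ 3 days", where the parenthesis limits Grade 4 neutropenia to episodes of at least 3 days.
- Bullet 2: "Any CTCAE Grade 3 toxicity other than Grade 3 lymphopenia". It has no neutropenia exemption and no duration limit.
- Bullet 3 concerns Grade 2 vomiting.
- Bullet 4 applies when the investigator or sponsor judges further escalation inappropriate for any reason.

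The explanatory text covers the vomiting criterion and lymphopenia ("The justification for the exemption of Grade 3 lymphopenia is based on the following"). It does not discuss neutropenia. For Cycle 1 it adds "Dosing will be discontinued based on DLT criteria noted above".

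For the escalation cohorts, the Synopsis says hematology "will be performed at screening, C1D8, C1D15, and at the beginning of each subsequent 28 day cycle". CBCs every two weeks start only after Cycle 1 (Section 13.8). Section 24.1 uses worst severity or grade for the AE and laboratory summaries and provides that "all events meeting the criteria of a DLT will be tabulated as a separate listing by subject and dose group". It does not say that DLTs are assigned by worst grade.

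**The concern.** A toxicity rule should not treat a worse event more leniently than a milder one. Taken together, bullets 1 and 2 either do that or leave the 3-day qualifier nearly empty, depending on a grading convention that is never stated for DLTs.

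DLT status decides whether a 3-patient cohort expands, whether a dose is abandoned, and where the MTD lies (Section 16.4). It also bears on the individual patient: Cycle 1 dosing stops on the DLT criteria, so two sites could handle the same short Grade 4 event differently. The toxicity class was anticipated. Section 7.1 singles out bone marrow effects in animals as the guide for escalation planning, with white-cell decreases roughly linear in dose. That makes neutropenia relevant but gives no human rate.

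**Working it through.** **1. The plan's own figures.** Tables 5 and 6 (Section 24.6) are the only stated numbers that use the DLT rate. At a DLT rate p = 0.30:

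- Table 5: (1-p)^3 = 0.343; 3p(1-p)^2 = 0.441; two or more = 1 - 0.343 - 0.441 = 0.216.
- Table 6: 0.441 × 0.343 = 0.151; 0.441 × (1 - 0.343) = 0.290.

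All cells reproduce at the five tabulated rates. They take p as given, so they do not depend on how neutropenia is classified.

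**2. The bullets applied to each case.**

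| Neutropenia event | By worst grade | If any Grade 3 value counts |
|---|---|---|
| Grade 3, any duration | DLT (bullet 2) | DLT (bullet 2) |
| Grade 4, at least 3 days | DLT (bullet 1) | DLT (bullet 1) |
| Grade 4, under 3 days | Not a DLT under bullets 1-3 | Normally a DLT (bullet 2), on the way into or out of Grade 4 |

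Only the last row differs. In the first column the rule is non-monotone in severity. In the second it is monotone, but the qualifier changes almost nothing.

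**3. Can duration be established?** The scheduled counts inside the 28-day window are C1D8 (±1 day) and C1D15 (±2 days). A Grade 4 value at one of them says nothing about how long it lasted. C2D1 is Day 29 ± 7 days (Section 13.7), so it cannot be relied on as a count within the window. Extra counts may follow from Section 13.9 ("If Grade 3 or 4 drug-related toxicity occurs, immediate treatment interruption will be followed by a selective dose reduction", after recovery to at least Grade 1) or Section 26.2 ("The investigator must follow-up on all drug-related AEs, SAEs, and other reportable information until the events have subsided"), but neither sets a time for a repeat count.

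**4. Illustrative size.** None of these inputs is in the documents; all are assumptions: undisputed DLT rate 15%; incidence q of Grade 4 neutropenia lasting d = 1 or 2 days, 1% to 5%; onset uniform over 28 days; only the two scheduled counts.

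- 3+3 acceptance: A(p) = (1-p)^3 + 3p(1-p)^2 × (1-p)^3. A(0.15) = 0.6141 + 0.1997 = 0.814.
- Chance that a d-day event coincides with a scheduled count: 2d/28 = 0.071 (d = 1) or 0.143 (d = 2).
- Recognised disputed rate r = q × 2d/28: lowest 0.01 × 0.0714 = 0.0007; highest 0.05 × 0.1429 = 0.0071.
- Acceptance if these are counted: A(0.1507) = 0.812; A(0.1571) = 0.5988 + 0.2005 = 0.799.
- Chance that a cohort holds at least one recognised disputed patient, 1-(1-r)^n: 0.2% to 2.1% for n = 3; 0.4% to 4.2% for n = 6.

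Under these assumptions the two readings differ by at most about 1.5 percentage points.

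**The case against.** The strongest reply is that the perverse result depends on a convention the protocol does not state for DLTs. The bullets are alternatives, and meeting any one suffices. If a Grade 3 value on the way to Grade 4 is enough, the event is a DLT, and the only fault is a redundant qualifier that errs towards safety. This stands as far as it goes: a reader might infer that the rule is definitely non-monotone, and the text supports that only under worst-grade classification. But the reading that avoids the problem empties the qualifier, and nothing in the protocol chooses between the two.

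Three further points limit the consequence.

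- **Discretion.** A reader might infer that no provision can classify a short Grade 4 event. That is too strong: bullet 4 sits inside the DLT list and can be used for it, and escalation decisions are taken jointly at teleconferences (Sections 9.1, 16.4). These allow a judgement but do not supply a rule.
- **Visibility.** A reader might infer that a disputed event would be invisible because the DLT listing holds only qualifying events. The laboratory tables by worst grade and dose group would show a Grade 4 count. They are not limited to Cycle 1 and show neither duration nor DLT handling, so they can raise the question without settling it.
- **Patient protection.** Interruption for related Grade 3-4 toxicity, the 28-day tolerability condition before escalation, and the smaller increments (up to 50%) after Grade 2 toxicity all apply whichever reading is used.

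Materiality is also fairly challenged. Had every short event been recognised, acceptance at 5% incidence would fall to A(0.20) = 0.709, about 10 points below 0.814. That is an upper bound for the assumed incidence, not evidence: the documents give neither the incidence nor the detection.

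**Conclusion.** The point holds as a minor defect in a stated decision rule. Grade 3 neutropenia of any duration counts; Grade 4 neutropenia under 3 days either escapes bullets 1 to 3 or makes the qualifier nearly void; and no section resolves this. The logic needs no assumption beyond the two readings.

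The size is unknown and may be nil. The shift from 0.814 to about 0.812-0.799 rests wholly on assumed rates and on two scheduled counts. A reader might go further and infer that the MTD or the 1000 mg/day dose is wrong. The documents do not support that: they do not say whether any short Grade 4 event occurred, and the Synopsis lets the recommended dose rest on toxicity, PK and convenience if no DLT is seen. The extension cohorts are dosed at the RP2D already set, so what remains is whether the reported DLT counts and the basis for that dose are the same under both readings.

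**What to change.** Make the rule monotone. The default is to drop the 3-day qualifier, so that any Grade 3 or higher neutropenia in Cycle 1 is a DLT. If brief neutropenia was meant to be tolerated, the alternative is to exempt Grade 3 neutropenia as well and require a repeat count within 3 days of a Grade 4 value.

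Because escalation is complete, apply the default in the report:

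1. State how Cycle 1 neutropenia was classified when cohort decisions were made.
2. Re-tabulate Cycle 1 DLTs by dose level, counting any Grade 3 or higher neutropenia, from blood counts already collected.
3. State whether any cohort decision, or the basis for the MTD or RP2D, changes.

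If there was no disputed event, one sentence closes the matter. The cost is one extra listing, a sentence or two of text, and possibly a slightly higher reported DLT count; no new data are needed. Section 29.0 puts every amendment through full review and approval, so correct Section 16.4 and the Synopsis only when they are next amended or the wording is reused.
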